13.2. Statistical Analyses

This is a safety study to determine Silverlon® dressing indication for radiation dermatitis. Descriptive statistics will be used to describe the study subject population. The primary analyses will evaluate the number of adverse events or reactions reported (if any) at the breast irradiation site where the Silverlon® dressing was applied. The primary analyses will be conducted on 30 fully evaluable subjects (i.e., 30 subjects that fully complete the study) and on all subjects that initiated treatment with Silverlon® dressing in an intent to treat analysis (see section 13.1). For a safety study, it is important to obtain the overall adverse event rate for all subjects that initiated treatment and all subjects who fully completed the study.

The secondary analyses will evaluate the compliance rates for the Silverlon® Dressing during RT and post RT. Compliance will be on the number of days during RT and post-RT that the dressing was worn. We expect compliance rate to be 97% (8). Additionally, we will evaluate the percentage of subjects that removed the dressing for sleeping. Subjects are asked to wear the dressing during sleep and only remove the dressing for RT sessions, showering/bathing, or swimming. Furthermore, we will calculate the number of hours during a day that the dressing was not worn summing the time between removal and application of the dressing each day.

Page 34 of 41 Version Date: 09/14/2021 Compliance will be evaluated in the 30 fully evaluable subjects. Although we can and will evaluate compliance in all subjects that initiated treatment, these analyses will not provide a complete picture of compliance due to early termination of study procedures. Furthermore, the secondary analyses will also evaluate withdrawal rates due to the Silverlon® dressing in all subjects who initiated treatment. We expect less than 6 subjects to withdraw due to the Silverlon® dressing. The exploratory analyses will assess trends in radiation dermatitis severity (i.e., RTOG and RISRAS) and quality of life (DLQI) during the course of the study. These analyses will also be able to evaluate changes in skin symptoms experience by the patient based on the RISRAS-Patient Symptom Scale during RT.

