1.3. OBJECTIVES

Primary Objective: To investigate the safety of Silverlon® dressing in patients throughout their prescribed course of radiation therapy and after radiation therapy.

- Hypothesis: We do not expect any adverse effects from extended use of Silverlon® dressing during and after radiation therapy.
- Primary Outcome Measures: Adverse reactions/events documented by the radiation oncologist as "probable" or "definite" related to Silverlon® Dressing (Weekly AE/Chart Review Source Doc).

Secondary Objective: To evaluate the feasibility of managing radiation dermatitis with Silverlon® dressing.

- Hypothesis: We expect that Silverlon® will be a feasible therapeutic modality for managing radiation dermatitis. We expect high compliance rate during RT and slightly lower when skin symptoms are not presented (i.e., before RT and post-RT). We do not expect any withdrawals due to adverse reactions to the dressing.
- Secondary Outcome Measures: Compliance; Withdrawal rate due to dressing.

Exploratory Objective: To monitor the severity of radiation dermatitis and patient quality of life during use of Silverlon® dressing throughout radiation therapy and after radiation therapy.

• Exploratory Outcome Measures: radiation dermatitis severity (RTOG Score & Radiation Induced Skin Reaction Assessment Scale (RISRAS)); DLQI

Page 7 of 41 RSRB STUDY00004587 Version Date: 09/14/2021 NCT04238728

[figure not shown]

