- Current hormone treatment (yes/no)
- Current Herceptin treatment (yes/no)
- Body Mass Index (BMI)
- Fitzpatrick Skin Type
- Surgery before RT (yes/no)
- Current Medications

Page 22 of 41 RSRB STUDY00004587 Version Date: 09/14/2021 NCT04238728 Weekly AE/Chart Review Source Doc: This is an electronic REDCap form for collection of any radiation treatment changes, skin changes, or adverse reactions documented by the treating radiation oncologist in the EMR chart note for the patient's weekly clinic visit. Study personnel will review the EMR chart note and report any documented any adverse reactions, skin changes, and/or radiation treatment changes in the form. The following information will be collected on the form:

- Changes in prescribed radiation treatment (yes/no; if "yes", then description of change)
- Documentation of skin changes in radiation treatment area (yes/no)
- Occurrence of adverse event in radiation treatment area to which Silverlon® dressing was applied
- Description of the adverse event
- Date of onset
- Serious (Yes/No)
- Intensity (Mild/Moderate/Severe)
- Relation to Study Drug (Definite/Probable/Possible/Unlikely/Unrelated)
- Action with Study Drug (No Action/Interrupted/Stopped Entirely).

Questions Log: This log will be an electronic REDCap form that collects the answers to the questions asked to the patient by phone, email, or in study visits (as preferred by the subject). Study personnel will ask the subject: 1) Are you wearing Silverlon dressing while you are sleeping? (yes/no); 2) Are you having any discomfort while wearing the Silverlon dressing? (yes/no); and 3) Are you having any adverse reactions to the Silverlon dressing? (yes/no). If the subject answers "yes" to question 3 regarding an adverse reaction to Silverlon, study personnel will document a description of this reaction in the space provided on the form.

RTOG Score: The RTOG toxicity criteria is one of the most commonly used scales for radiation-induced skin reactions (21, 22). The radiation oncologist will rate the skin reaction in the area where Silverlon® dressing was applied in person using the RTOG scale below. The RTOG scores will completed on paper and then entered electronically into REDCap:

RTOG SCALE

0	1	2	3	4	5
No change	Faint erythema,	Tender or bright	Confluent moist	Ulceration,	Death
	dry	erythema,	desquamation in	hemorrhage,	
	desquamation,	moderate	areas other than	necrosis	
	epilation,	edema, patchy	in skin folds,		

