9. RISK/BENEFIT ASSESSMENT

9.1. POTENTIAL RISKS

The proposed study is a low risk safety clinical trial. The only patient intervention in this study is the application of Silverlon® dressings to the radiation site. No adverse reactions or events have been reported for Silverlon® dressings. Subjects may find the dressing uncomfortable to wear inside the bra. However, discomfort while wearing has not been reported. Unexpected side effects, such as allergic reactions, may occur and are unpredictable. This reaction may be mild, such as a skin rash, or you may have more severe symptoms like swelling of the throat, low blood pressure, and shortness of breath. If any of these unexpected side effects occur, subjects will be advised to stop use of their intervention immediately. Subjects will be informed about any additional potential risks if they are discovered. Furthermore, while we make every effort to keep all data and study information private, this cannot be guaranteed. All data will be de-identified and stored in a locked file in a locked office. All appropriate procedures will be taken to maintain subject privacy and data collected during this study.

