10. SAFETY AND REPORTABLE EVENTS

10.1. ADVERSE EVENT MONITORING

This is a safety study to determine if Silverlon® dressing can be indicated for radiation dermatitis. The primary outcome is not clinical response to treatment; it is safety (i.e., adverse reactions/events/complications). Any adverse event will be documented on the AE Source Doc throughout the course of the study. Any safety information for an individual patient that is volunteered by a study subject during the course of this research must be reported as described below:

All adverse events, whether observed by the Investigator radiation oncologist, or nurse, elicited from, or volunteered by the subject, will be documented. Each adverse event will be recorded on the electronic AE Source Doc. This form will record the will include a brief description of the experience, the date of onset, the date of resolution, the duration and type of experience, the severity, contributing factors, and any actions taken. This description will be in the summary not during a subject's regularly scheduled clinic appointment.

Adverse event (AE): is any untoward medical occurrence in a subject using study device, and which does not necessarily have a causal relationship with this treatment. An adverse event can be any unfavorable and unintended sign (including abnormal laboratory test results), symptom, or disease temporally associated with the use of the study device, whether or not considered related to the study device. The relationship of each adverse event to the study device must be recorded as one of the choices on the scale described below.

Attribution: An assessment of the relationship between the adverse event and the protocol treatment, using the following categories.

ATTRIBUTION	DESCRIPTION
Unrelated	The AE is clearly NOT related to treatment.
Unlikely	The AE is doubtfully related to treatment.
Possible	The AE may be related to treatment.
Probable	The AE is likely related to treatment.
Definite	The AE is clearly related to treatment

Page 30 of 41 RSRB STUDY00004587 Version Date: 09/14/2021 NCT04238728 **Hospitalization (or prolongation of hospitalization):** For AE reporting purposes, a hospitalization is defined as an inpatient hospital stay equal to or greater than 24 hours. **Life Threatening Adverse Event:** Any AE that places the subject at immediate risk of death from the AE as it occurred.

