13. DATA ANALYSIS AND MONITORING

13.1. Sample Size Justification

The study will recruit 36 total subjects to accrue 30 fully evaluable subjects with an estimated 20% withdrawal rate. The target enrollment table in §3.9 shows that we have access to enough eligible patients to complete this study in 12 months. The following table shows the

Page 33 of 41 RSRB STUDY00004587 Version Date: 09/14/2021 NCT04238728 precision estimates and 95% confidence intervals for our primary objective (i.e., adverse events related to Silverlon®) and secondary objective (i.e., compliance and withdrawal rate). Our estimates for adverse events (primary and intent to treat analyses) are based on published trials showing no reported adverse events or allergic reactions to silver nylon dressing in patients receiving radiation (8, 15-17). Our estimates for the primary objective were conducted with sample size of 30 for the fully evaluable subjects and 36 for all subjects that initiated treatment. Our estimates for compliance (secondary analyses) are based on the Aquinos-Parsons et al study in breast cancer patients that showed a 97% compliance rate for silver nylon dressing (8). Our estimates for compliance were conducted using sample size of 30 for fully evaluable subjects. In subjects that withdraw from the study, we will be able to partially evaluate compliance because of their early termination of treatment and study procedures. Our estimates for withdrawal are based on the Vavassis et al study in head & neck cancer patients using silver nylon dressing that reported 1 of 12 subjects (i.e., 8%) withdrew from the study (17). Our estimates for withdrawal were conducted using a sample size of 36 to capture all subjects that initiated treatment. 95% Exact Clopper Pearson confidence intervals on the expected proportion have been generated using SAS 9.4.

95% Confidence Intervals								
Objective	Measure	Sample Size	Proportion Estimate	Expected Observed Count	95% LCL	95% UCL		
Primary	# Adverse Events per number of patients	30	0	0	0	0.116		
Intent to Treat	# Adverse Events per number of patients	36	0	0	0	0.097		
Secondary	Compliance	30	0.97	29	0.828	0.999		
Secondary	Withdrawal	36	0.166	6	0.064	0.328		

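### The documents disagree on whether the primary safety endpoint covers only events under the dressing or any event related to the dressing, and section 13.2 read literally leaves out a related systemic reaction.

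*Combined protocol and SAP*

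**What the plan says.** Section 13.2 is where the analysis is stated. It sets the primary count as the "number of adverse events or reactions reported (if any) at the breast irradiation site where the Silverlon® dressing was applied". Two other places are limited in a similar way. The Weekly AE/Chart Review Source Doc in section 5.3 has a field for "Occurrence of adverse event in radiation treatment area to which Silverlon® dressing was applied". Section 11 defines an adverse event, for this study, as radiation dermatitis of RTOG grade 4 or above, or another reaction of grade 3 or higher in the dressed area.

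Other places set no body-site limit:

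- Section 1.3 gives the primary outcome measure as "Adverse reactions/events documented by the radiation oncologist as 'probable' or 'definite' related to Silverlon® Dressing".
- Section 13.1 tabulates precision estimates and "95% confidence intervals for our primary objective (i.e., adverse events related to Silverlon".
- Section 10.1 defines the term broadly: "An adverse event can be any unfavorable and unintended sign (including abnormal laboratory test results), symptom, or disease temporally associated with the use" of the device. It sends every adverse event to the AE Source Doc, and section 10.2 sends all side effects and adverse reactions there too.
- Section 7 says that an allergic reaction to the dressing goes on the AE Source Doc.

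Section 9.1 says that allergic reactions may occur, ranging from a mild rash to "more severe symptoms like swelling of the throat, low blood pressure, and shortness of breath".

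**The concern.** The defined outcome and the analysed outcome are different sets of events. A reaction with throat swelling or low blood pressure, judged definite, meets section 1.3 but did not occur at the breast site, so the 13.2 sentence does not count it. Nothing says which section governs.

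Safety is the only primary question, the plan expects zero events, and section 14 says that composite data go to the FDA in support of a 510(k) application. A report that follows 13.2 to the letter could show no primary events although an event judged related to the dressing had occurred. If the scope is settled only after such an event, the choice is made with the result known.

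**Working it through.** **1. The passages side by side.** Take one subject with a systemic allergic reaction, no local event, rated definite.

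| Place | Scope | Is this event covered? |
|---|---|---|
| 1.3 primary outcome | Probable or definite, any site | Yes |
| 13.1 primary objective | Related to the dressing, any site | Yes |
| 7, 10.1, 10.2 recording rules | All adverse events and allergic reactions | Yes, recorded |
| 13.2 analysis sentence | Site under the dressing | No |
| 5.3 form, occurrence field | Site under the dressing | No |
| 11 definition | Dressed area, with a grade limit | No |

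I take the AE Source Doc of sections 7 and 10 to be the Weekly AE/Chart Review Source Doc, the only adverse-event form listed in section 14.

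**2. The plan's own figures.** Section 13.1 uses two-sided 95% exact Clopper-Pearson limits with n = 30 (fully evaluable) and n = 36 (initiated treatment). With zero events the upper limit is 1 − 0.025^(1/n).

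- n = 30: 1 − 0.025^(1/30) = 0.1157; the plan states 0.116.
- n = 36: 1 − 0.025^(1/36) = 0.0974; the plan states 0.097.

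Both reproduce. They assume zero events, so they do not depend on the site limit.

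**3. Effect of the scope on an observed result.** For x events in n subjects the limits are the 0.025 quantile of Beta(x, n − x + 1) and the 0.975 quantile of Beta(x + 1, n − x). The values of x are assumed, with one event per affected subject, because the documents give no rate of systemic reactions.

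| Systemic related events among 36 initiators | Counted | Left out by the site limit |
|---|---|---|
| 1 | 1/36 = 2.8% (0.07% to 14.5%) | 0/36 (0 to 9.7%) |
| 2 | 2/36 = 5.6% (0.7% to 18.7%) | 0/36 (0 to 9.7%) |

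**4. The fully evaluable set.** Section 3.1 requires dressing use to continue until two weeks after radiation therapy. Section 7 lists allergic reaction among the reasons for withdrawal and says that withdrawn subjects are replaced. If the affected subject completes, this set shows 1/30 = 3.3% (0.08% to 17.2%) when the event is counted. If she is withdrawn and replaced, it shows 0/30 (upper limit 11.6%) whatever the scope.

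**The case against.** The strongest reply is that the event is neither lost nor barred from the primary result. Section 1.3 would count it. Section 13.1, to which 13.2 refers, describes the primary objective without a site limit. Section 13.2 itself adds that "it is important to obtain the overall adverse event rate for all subjects that initiated treatment and all subjects who fully completed the study". Sections 7, 10.1 and 10.2 place the event on the adverse-event form, whose general purpose is "collection of any radiation treatment changes, skin changes, or adverse reactions documented by the treating radiation oncologist in the EMR chart note". Withdrawal due to the dressing is a secondary outcome in all initiators, and serious events are reported under section 10.3.

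Most of this stands, and it rules out three stronger readings that a reader might infer:

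- That a systemic reaction cannot enter the primary result, or that the form holds only local events. The unrestricted passages above contradict both.
- That a rash spreading outward from the dressed breast is also lost. It involves the dressed site, so 13.2 still counts it.
- That the protocol ranks systemic allergy as the gravest device risk. Section 9.1 describes more severe symptoms of an unpredictable reaction and ranks nothing.

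The reply does not remove the conflict. Recording an event is not the same as counting it. The sentence on the overall rate explains why two populations are analysed; at most it makes 13.2 ambiguous. An analyst who follows 13.2, the form field and section 11 would reach the site-limited count in good faith.

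**Conclusion.** The point holds as a conflict between stated rules on the anatomical scope of the primary endpoint, not as a proven exclusion. Sections 13.2, 11 and the form field point one way; sections 1.3, 13.1, 7, 10.1 and 10.2 point the other. Read literally, 13.2 omits from the primary count a related systemic reaction that 1.3 includes.

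For one such event, the upper limit reported in initiators moves between 9.7% and 14.5%, and the point estimate between 0 and 2.8%. This rests on an assumed count and on the planned 36 initiators. It shows how sensitive the result is to a single event, and does not predict that one will occur.

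**What to change.** 1. In 13.2, define the primary count as any adverse event, local or systemic, rated probable or definite related to the dressing. Report location (under the dressing, or elsewhere/systemic) as a descriptor. Write the 1.3 threshold into the sentence: a bare reference to attribution under section 10.2 would leave five categories open.
2. On the weekly form, change the field to the occurrence of any adverse event and add a location field.
3. Reconcile the section 11 definition with 1.3 and 10.1 for the purpose of counting the endpoint. Section 11 also ties its definition to withdrawal; that clinical use is for the sponsor and investigator to settle, and no change to it is proposed here.
4. State that the result is read mainly in all subjects who initiated treatment, because replacement can remove the affected subject from the fully evaluable set.

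The cost is a few lines of text and a small change to one REDCap form, with no change in sample size or visits. The downside is that the reported rate may be slightly less favourable, since related events away from the dressing are added.

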11. DATA AND SAFETY MONITORING PLAN

[name] (co-investigator) in Radiation Oncology at University of Rochester will serve as the Clinical Monitor for this study. Approval of protocol, informed consent

Page 32 of 41 RSRB STUDY00004587 Version Date: 09/14/2021 NCT04238728 procedures, and recruitment will be obtained from the University RSRB. Any safety concerns about the clinical protocol will be brought to the immediate attention of the Principal Investigator and Co-investigator. Study personnel will follow aforementioned reporting procedures for adverse event reporting, including any serious adverse events. Protocol deviations and quality issues will be recorded and reported to the IRB per local policies. Remedial and/or corrective action to prevent reoccurrence of protocol deviations or quality issues will be instituted as necessary. Because this study's procedures pose relatively low risk to subjects, monthly data and procedural reviews by the Clinical Monitor and Investigator in consultation with study personnel will be sufficient to identify and ameliorate any potential safety issues. As such, an additional Data and Safety Monitoring Plan document will be not be created for this study.

Patients will have their radiated sites examined once a week by either a radiation oncologist as part of their regular course of radiation therapy. At this examination, any adverse events related to their skin will be recorded. For the purpose of this study, an adverse event will be defined as severe radiation dermatitis meeting the definition of RTOG score grade 4 or above (ulceration, hemorrhage or necrosis) or other adverse reaction of Grade 3 or higher in the area of radiation area where Silverlon® dressing is applied. Patients meeting the definition of 'adverse event' will be withdrawn from the study and the radiation dermatitis then treated according to local protocol as ordered by the attending radiation oncologist. Changes in dose or scheduling of radiation therapy in response to an adverse event will remain the responsibility of the attending radiation oncologist.

If a patient feels that they are having an adverse event outside of the weekly monitoring schedule, they may contact the study coordinator or principal investigator by phone and an immediate follow-up appointment with the radiation oncologist will be arranged.

12. STUDY MONITORING PLAN – Sponsor

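### The only adverse-event row labelled 'Primary' is the 30-completer row, which by the plan's own withdrawal rule cannot contain severe dressing-site events found before the 2-week visit; the all-initiated rate should be named as the lead

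*Combined protocol and SAP*

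**What the plan says.** - **Analysis sets.** Section 13.2 states that the primary safety analysis "will be conducted on 30 fully evaluable subjects (i.e., 30 subjects that fully complete the study) and on all subjects that initiated treatment". It adds that "it is important to obtain the overall adverse event rate for all subjects that initiated treatment and all subjects who fully completed the study". No order is given.
- **Labels.** The text of section 13.1 puts both sizes under the primary objective: "Our estimates for the primary objective were conducted with sample size of 30 for the fully evaluable subjects and 36" for all who started treatment. The same section also separates the two terms: "Our estimates for adverse events (primary and intent to treat analyses". In its table the n=30 adverse-event row is labelled Primary and the n=36 row Intent to Treat.
- **Who is a completer.** Under section 3.1 a fully evaluable subject must continue to two weeks after radiation therapy and complete all procedures. Subjects who start and then withdraw go to the intent-to-treat analyses.
- **Withdrawal.** In section 11, "an adverse event will be defined as severe radiation dermatitis meeting the definition of RTOG score grade 4 or above", or another reaction of Grade 3 or higher where the dressing lies. It continues: "Patients meeting the definition of 'adverse event' will be withdrawn from the study". Section 7 has withdrawn subjects stop the dressing and replaces them.
- **What is counted.** Section 13.2 counts the "number of adverse events or reactions reported (if any) at the breast irradiation site". Section 1.3 limits the primary outcome to events that the radiation oncologist calls probably or definitely related.

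**The concern.** Safety is the primary objective, and composite data are to go to the FDA in support of a 510(k) application (section 14). A headline rate from completers comes from a group whose membership depends on the outcome: a subject with a section 11 event leaves the group and a replacement refills it to 30. If the row labelled Primary is carried forward as the main result, it will understate severe events at the dressing site.

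Two related gaps weaken the rate that should lead. First, no section expressly continues study adverse-event capture after withdrawal. Section 10.2 runs monitoring to completion of the study, section 10.3 reports serious events until the subject completes it, and the 90-day contact is arranged at the 2-week visit (section 5.1), which a withdrawn subject may not attend. Second, sections 1.3, 10.1, 11 and 13.2 describe the event differently, so the numerator is not fixed for either population.

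**Working it through.** **1. Reproduce the plan's table.** Section 13.1 specifies exact two-sided 95% Clopper-Pearson intervals. For x events in n subjects, the lower limit is the 0.025 quantile of Beta(x, n − x + 1) and the upper limit is the 0.975 quantile of Beta(x + 1, n − x). With x = 0 the lower limit is 0 and the upper limit is 1 − 0.025^(1/n).

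- n = 30: 1 − 0.025^(1/30) = 0.1157 (plan: 0.116)
- n = 36: 1 − 0.025^(1/36) = 0.0974 (plan: 0.097)

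Both agree. With no events, the all-initiated set gives the tighter upper limit.

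**2. Trace a section 11 event through the rules.**

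- Detection during treatment: "Patients will have their radiated sites examined once a week by either a radiation oncologist as part of their regular course of radiation therapy". An event during radiation therapy would therefore normally be found before the 2-week post-RT visit.
- Section 11 then requires withdrawal. Its wording is mandatory, whereas section 7 only permits withdrawal for RTOG 3 or an allergic reaction.
- The subject stops the dressing (section 7) and so does not continue to two weeks after radiation therapy (section 3.1). She is not fully evaluable, and a replacement is recruited.
- She remains in the all-initiated set (section 3.1).

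So a section 11 event found before the 2-week visit counts in the n=36 row and cannot count in the n=30 row.

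**3. Size.** The plan expects 36 starters and 30 completers, so 36 − 30 = 6 non-completers. Let k of the 6 be withdrawn for a section 11 event before the 2-week visit. Assumptions: k is illustrative, with no rate in the documents behind it; each event is judged probably or definitely related, so that it counts under section 1.3; there is one event per subject; and no other event is counted.

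| k | Row labelled Primary | All initiated |
|---|---|---|
| 0 | 0/30 (0 to 11.6%) | 0/36 (0 to 9.7%) |
| 1 | 0/30 (0 to 11.6%) | 1/36 = 2.8% (0.1 to 14.5%) |
| 2 | 0/30 (0 to 11.6%) | 2/36 = 5.6% (0.7 to 18.7%) |
| 3 | 0/30 (0 to 11.6%) | 3/36 = 8.3% (1.8 to 22.5%) |
| 6 | 0/30 (0 to 11.6%) | 6/36 = 16.7% (6.4 to 32.8%) |

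The completer row does not change with k. The number treated may also exceed 36, because withdrawals are replaced. At a true 20% withdrawal rate, 30/0.8 = 37.5, so 38 are needed; 3/38 = 7.9% (1.7 to 21.4%). The contrast is much the same.

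**4. Compare the event definitions.**

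- Section 1.3: related events only (probable or definite), no minimum grade.
- Section 10.1: any untoward occurrence, related or not.
- Section 11: severe events under the dressing, with no attribution test.
- Section 13.2: events or reactions at the irradiation site.

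A grade 4 skin reaction attributed wholly to radiation is an event under section 11 but not under section 1.3.

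**The case against.** The strongest reply is that the right analysis is already planned. Section 13.2 runs the primary analysis on all initiators as well as completers, and section 3.1 places withdrawn subjects there. The study is descriptive and single-arm, and no decision threshold turns on which rate leads. The label sits in a planning table, not a results shell.

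The events that cause withdrawal are also visible elsewhere. Section 7 sends RTOG 4 or above and allergic reactions to the adverse-event form, and requires the date and reason for every withdrawal. Section 13.2 analyses dressing-related withdrawal in all who started. After withdrawal, patients keep routine oncology care (section 7), and the sponsor's monitor reviews records for end-point events (section 12).

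All of this stands, and it rules out three stronger readings that a reader might infer:

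- **That severe events are lost, or that the plan analyses completers only.** They are recorded and enter a planned primary rate. The follow-up gap concerns later events in withdrawn subjects, not the event that led to withdrawal.
- **That completers can show no reactions.** Milder events without withdrawal, temporary interruptions, and events first seen at the 2-week visit or later can still count among them.
- **That the study's chance of detecting a severe event can be shown to fall by a stated amount.** That needs the share of events first seen at the 2-week visit, which the documents do not give. Spreading events evenly over wear would have no support and would ignore the 7-day contacts that continue to study completion. In any case, no detection is lost while the all-initiated rate is reported.

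The reply does not remove the label itself: the one adverse-event row called Primary is the one selected on the outcome, and no section says otherwise.

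**Conclusion.** The point holds as a matter of labelling and follow-up. The completer rate is biased low for section 11 events found before the 2-week visit. This follows from sections 3.1, 7 and 11 read together and needs no assumed rate. How far it falls short depends on how many such events occur and on whether they are judged probably or definitely related, neither of which the documents supply. In the illustration with three events the gap is 0/30 against 3/36 (8.3%). With none, the all-initiated upper limit is the better one, 9.7% against 11.6%. Since both rates are planned, this is a correction of modest weight that should still be made, because the headline safety figure is what will be read outside the trial.

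**What to change.** 1. In sections 13.1 and 13.2, name all subjects who initiated the dressing as the lead primary safety population (planning row 0/36, upper limit 9.7%). Relabel the table rows to match and describe the completer rate as supportive.
2. State that adverse-event chart review and the 90-day contact continue for withdrawn subjects who agree.
3. Reconcile the event definition in section 11 with the primary outcome in section 1.3, and with sections 10.1 and 13.2, so that one definition drives the primary count. Which clinical definition or withdrawal rule to use is for the investigators and sponsor; this review does not propose one.

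The cost is wording, plus chart review and one contact for about six withdrawn subjects. No new analysis set is needed. The downside is a headline rate that may look less favourable.
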